11.2 Database management and quality control

Novartis personnel (or designated CRO) will review the data entered by investigational staff for completeness and accuracy. Electronic data queries stating the nature of the problem and requesting clarification will be created for discrepancies and missing values and sent to the investigational site via the EDC system. Designated investigator site staff are required to respond promptly to queries and to make any necessary changes to the data.

Concomitant treatments and prior medications entered into the database will be coded using the World Health Organization (WHO) Drug Reference List, which employs the Anatomical Therapeutic Chemical classification system. Medical history/current medical conditions and adverse events will be coded using the Medical Dictionary for Regulatory Activities (MedDRA) terminology.

Dates of screenings, randomizations, screen failures and study completion, as well as randomization codes and data about all study treatment (s) dispensed to the participant and all dosage changes will be tracked using an Interactive Response Technology (IRT). The system will be supplied by a vendor, who will also manage the database. The data will be sent electronically to Novartis (or a designated CRO) at specific timelines.

Each occurrence of a code break via IRT will be reported to the clinical team and monitor. The code break functionality will remain available until study shut down or upon request of Novartis.

Once all the necessary actions have been completed and the database has been declared to be complete and accurate, it will be locked **and the treatment codes will be unblinded** and made available for data analysis. Any changes to the database after that time can only be made after written agreement by Novartis development management.

11.3 Site monitoring

Before study initiation, at a site initiation visit or at an investigator's meeting, a Novartis representative will review the protocol and data capture requirements (i.e. eSource DDC or eCRFs) with the investigators and their staff. During the study, Novartis employs several methods of ensuring protocol and GCP compliance and the quality/integrity of the sites' data. The field monitor will visit the site to check the completeness of participant records, the accuracy of data capture / data entry, the adherence to the protocol and to Good Clinical Practice, the progress of enrollment, and to ensure that study treatment is being stored, dispensed, and accounted for according to specifications. Key study personnel must be available to assist the field monitor during these visits. Continuous remote monitoring of each site's data may be performed by a centralized Novartis CRA organization. Additionally, a central analytics organization may analyze data & identify risks & trends for site operational parameters, and provide reports to Novartis clinical teams to assist with trial oversight.

The investigator must maintain source documents for each participant in the study, consisting of case and visit notes (hospital or clinic medical records) containing demographic and medical information, laboratory data, electrocardiograms, and the results of any other tests or assessments. All information on CRFs must be traceable to these source documents in the participant's file. The investigator must also keep the original informed consent form signed by the participant (a signed copy is given to the participant).

The investigator must give the monitor access to all relevant source documents to confirm their consistency with the data capture and/or data entry. Novartis monitoring standards require full verification for the presence of informed consent, adherence to the inclusion/exclusion criteria, documentation of SAEs, and of data that will be used for all primary variables. Additional checks of the consistency of the source data with the CRFs are performed according to the study-specific monitoring plan. No information in source documents about the identity of the participants will be disclosed.

12 Data analysis and statistical methods

Any data analysis carried out independently by the investigator should be submitted to Novartis before publication or presentation.

12.1 Analysis sets

For all analysis sets, participants will be analyzed according to the study treatment(s) received. The safety analysis set will include all participants that received any study drug.

The full analysis set (FAS) will include all randomized participants.

Commercially Confidential Information

12.2 Participant demographics and other baseline characteristics

Baseline will be defined as the last non-missing assessment prior to the first dose of study drug, unless specified otherwise.

Demographic and other baseline data including disease characteristics will be listed and summarized descriptively by treatment group for safety analysis set. Categorical data will be presented as frequencies and percentages. For continuous data, mean, standard deviation, median, minimum, and maximum will be presented. Relevant medical histories and current medical conditions at baseline will be summarized by system organ class and preferred term, by treatment group.

12.3 Treatments

Concomitant medications and significant non-drug therapies prior to and after the start of the study treatment will be listed and summarized according to the Anatomical Therapeutic Chemical (ATC) classification system, by treatment group for the FAS.

12.4 Analysis of the primary endpoint(s)/estimand(s)

The primary objectives of the study include assessing the efficacy of MBL949 in reducing weight and evaluating its safety and tolerability.

12.4.1 Definition of primary endpoint(s)/estimand(s)

The primary endpoint for efficacy is change-from-baseline in weight at week 16. Baseline weight is defined as the last weight measurement before dosing. Primary endpoints for safety and tolerability are occurrences and severities of adverse events.

12.4.2 Statistical model, hypothesis, and method of analysis

Commercially Confidential Information

12.4.3 Safety endpoints

For all safety analyses, the safety set will be used. All listings and tables will be presented by treatment group.

Adverse events

All information obtained on adverse events will be displayed by treatment group and participant.

The number (and percentage) of participants having treatment emergent adverse events (events started after the first dose of study medication or events present prior to start of treatment but increased in severity based on preferred term) will be summarized in the following ways:

- by treatment, primary system organ class and preferred term.
- by treatment, primary system organ class, preferred term and maximum severity.
- by treatment, Standardized MedDRA Query (SMQ) and preferred term.

Separate summaries will be provided for study medication related adverse events, death, serious adverse events, and other significant adverse events leading to discontinuation.

A participant with multiple adverse events within a primary system organ class is only counted once towards the total of the primary system organ class.

Vital signs

All vital signs data will be listed by treatment group, participant, and visit/time and if ranges are available, abnormalities (and relevant orthostatic changes) will be flagged. Summary statistics will be provided by treatment and visit/time.

12-lead ECG

PR, QRS, QT, QTcF, RR intervals and HR will be obtained from 12-lead ECGs for each participant during the study. ECG data will be read and interpreted locally.

Abnormal ECG, especially HR, will be flagged and listed by treatment group, participant and visit/time. Summary statistics of all ECG data will be provided by treatment and visit/time. Categorical analyses of QT/QTc, PR, QRS, QRS, RR intervals and HR data based on the number of participants meeting or exceeding predefined limits, in terms of absolute values or changes from baseline, will be presented. In addition, a listing of these participants will be produced by treatment group.

Clinical laboratory evaluations

If normal ranges are available, abnormal laboratory data will be flagged and listed by treatment group, participant, and visit/time. Summary statistics of select laboratory parameters will be provided by treatment group and visit/time.

Commercially Confidential Information

Commercially Confidential Information

12.4.5 Handling of missing values not related to intercurrent event

All participants with a baseline weight and at least one post-baseline weight measurement will be included in the primary analysis. Commercially Confidential Information

12.4.6 Sensitivity analyses for primary endpoint/estimand

Commercially Confidential Information

12.4.7 Supplementary analysis

Commercially Confidential Information

12.4.8 Supportive analyses

To evaluate the effect of intercurrent events on efficacy/safety results, primary analysis may be performed on FAS including/excluding some intercurrent events cases described in [Section 12.4.4](#) as seen fit.

12.5 Analysis of secondary endpoints/estimands

None.

12.6 Analysis of exploratory endpoints

Commercially Confidential Information

Commercially Confidential Information

12.7 Interim analyses

Commercially Confidential Information

12.8 Sample size calculation

12.8.1 Primary endpoint(s)

Commercially Confidential Information

At final analysis, MBL949 arms 1, 2, and 3 (if not terminated early) will each have 12 participants, and the placebo arm will have at least 24 participants who complete week 16 weight assessment. Therefore, MBL949 efficacy group will have a sample size of either 24 or 36. Conservatively assuming that the efficacy group and placebo arm each has 24 participants, the power for efficacy criteria is still 95%.

At final analysis, if MBL949 arm 5 has been triggered and completed, the weight change of this arm will be compared to MBL949 efficacy group.

Commercially Confidential Information

Weight change in MBL949 arm 4 will be compared against placebo arm and MBL949 efficacy group, respectively. Assuming that the true weight change in MBL949 arm 4 is -2kg, there is at least a 77% probability of declaring MBL949 arm 4 having more weight loss than placebo, and at least a 99% probability of declaring MBL949 efficacy group having more weight loss than MBL949 arm 4, given sample sizes of 12, ≥ 24 , and ≥ 24 in MBL949 arm 4, MBL949 efficacy group, and placebo arm, respectively, where type I error rate is 0.1.

Commercially Confidential Information

13 Ethical considerations and administrative procedures

13.1 Regulatory and ethical compliance

This clinical study was designed and shall be implemented, executed and reported in accordance with the ICH Harmonized Tripartite Guidelines for Good Clinical Practice, with applicable local regulations (including European Directive 2001/20/EC, US CFR 21), and with the ethical principles laid down in the Declaration of Helsinki.

13.2 Responsibilities of the investigator and IRB/IEC

Before initiating a trial, the investigator/institution must obtain approval/favorable opinion from the Institutional Review Board/Independent Ethics Committee (IRB/IEC) for the trial protocol, written informed consent form, consent form updates, participant recruitment procedures (e.g., advertisements) and any other written information to be provided to participants. Prior to study start, the investigator is required to sign a protocol signature page confirming his/her agreement to conduct the study in accordance with these documents and all of the instructions and procedures found in this protocol and to give access to all relevant data and records to Novartis monitors, auditors, Novartis Quality Assurance representatives, designated agents of Novartis, IRBs/IECs, and regulatory authorities as required. If an inspection of the clinical site is requested by a regulatory authority, the investigator must inform Novartis immediately that this request has been made.

13.3 Publication of study protocol and results

The protocol will be registered in a publicly accessible database such as clinicaltrials.gov and as required in EudraCT. In addition, after study completion (defined as last patient last visit) and finalization of the study report the results of this trial will be submitted for publication and

posted in a publicly accessible database of clinical trial results, such as the Novartis clinical trial results website and all required Health Authority websites (e.g. Clinicaltrials.gov, EudraCT etc.).

For details on the Novartis publication policy including authorship criteria, please refer to the Novartis publication policy training materials that were provided to you at the trial investigator meetings.

13.4 Quality Control and Quality Assurance

Novartis maintains a robust Quality Management System (QMS) that includes all activities involved in quality assurance and quality control, to ensure compliance with written Standard Operating Procedures as well as applicable global/local GCP regulations and ICH Guidelines.

Audits of investigator sites, vendors, and Novartis systems are performed by auditors, independent from those involved in conducting, monitoring or performing quality control of the clinical trial. The clinical audit process uses a knowledge/risk based approach.

Audits are conducted to assess GCP compliance with global and local regulatory requirements, protocols and internal SOPs, and are performed according to written Novartis processes.

13.5 Participant Engagement

The following participant engagement initiatives are included in this study and will be provided, as available, for distribution to study participants at the time points indicated. If compliance is impacted by cultural norms or local laws and regulations, sites may discuss modifications to these requirements with Novartis.

- Thank You letter
- Plain language trial summary - after CSR publication

14 Protocol adherence

This protocol defines the study objectives, the study procedures and the data to be collected on study participants. Additional assessments required to ensure safety of participants should be administered as deemed necessary on a case by case basis. Under no circumstances including incidental collection is an investigator allowed to collect additional data or conduct any additional procedures for any purpose involving any investigational drugs under the protocol, other than the purpose of the study. If despite this interdiction prohibition, data, information, observation would be incidentally collected, the investigator shall immediately disclose it to Novartis and not use it for any purpose other than the study, except for the appropriate monitoring on study participants.

Investigators ascertain they will apply due diligence to avoid protocol deviations. If an investigator feels a protocol deviation would improve the conduct of the study this must be considered a protocol amendment, and unless such an amendment is agreed upon by Novartis and approved by the IRB/IEC and Health Authorities, where required, it cannot be implemented.

16.1 Appendix 1: Clinically notable laboratory values and vital signs

Clinically notable values for vital signs are as follows:

- Any significant increase or decrease in vital signs beyond inclusion/exclusion criteria:
 - Systolic blood pressure less than 95 mgHg or greater than 155 mgHg
 - Diastolic blood pressure less than 60 or greater than 95 mgHg
 - Pulse rate less than 56 or greater than 110 bpm

If these clinically notable vital signs are observed, investigators should initiate appropriate, guideline directed clinical care and inform the Sponsor.

16.2 Appendix 2: Liver event and laboratory trigger definitions & follow-up requirements

Table 16-1 Liver event and laboratory trigger definitions

	Definition/ threshold
Liver laboratory triggers If ALT, AST and total bilirubin normal at baseline:	
 ALT or AST > 5 × ULN ALP > 2 × ULN (in the absence of known bone pathology) Total bilirubin > 3 × ULN (in the absence of known Gilbert syndrome) ALT or AST > 3 × ULN and INR > 1.5 Potential Hy's Law cases (defined as ALT or AST > 3 × ULN and Total bilirubin > 2 × ULN [mainly conjugated fraction] without notable increase in ALP to > 2 × ULN) Any clinical event of jaundice (or equivalent term) ALT or AST > 3 × ULN accompanied by (general) malaise, fatigue, abdominal pain, nausea, or vomiting, or rash with eosinophilia Any adverse event potentially indicative of a liver toxicity*
If ALT or AST abnormal at baseline:	
 ALT or AST > 2x baseline or > 300 U/L (whichever occurs first)
*These events cover the following: hepatic failure, fibrosis and cirrhosis, and other liver damage-related conditions; non-infectious hepatitis; benign, malignant and unspecified liver neoplasms ULN: upper limit of normal	

Table 16-2 Follow up requirements for liver laboratory triggers with liver symptoms

	ALT	TBL	Liver Symptoms	Action
ALT increase without bilirubin increase:				
	
If normal at baseline: ALT > 3 × ULN
 
If elevated at baseline: ALT > 2 x baseline or > 300 U/L (whichever occurs first)
	
Normal
 
For patients with Gilbert's syndrome: No change in baseline TBL
	None	
 No change to study treatment Measure ALT, AST, ALP, GGT, TBIL, INR, albumin, CK, and GLDH in 48-72 hours. Follow-up for symptoms.

	ALT	TBL	Liver Symptoms	Action
	
If normal at baseline: ALT > 5 x ULN for more than two weeks
 
If elevated at baseline: ALT > 3 x baseline or > 300 U/L (whichever occurs first) for more than two weeks
	
Normal
 
For patients with Gilbert's syndrome: No change in baseline TBL
	None	
 • Interrupt study drug • Measure ALT, AST, ALP, GGT, TBIL, INR, albumin, CK, and GLDH in 48-72 hours. • Follow-up for symptoms. • Initiate close monitoring and workup for competing etiologies. • Study drug can be restarted only if another etiology is identified and liver enzymes return to baseline.
	
If normal at baseline: ALT > 8 x ULN
	Normal	None	
ALT increase with bilirubin increase:				
	
If normal at baseline: ALT > 3 x ULN
 
If elevated at baseline: ALT > 2 x baseline or > 300 U/L (whichever occurs first)
	
TBL > 2 x ULN (or INR > 1.5)
 
For patients with Gilbert's syndrome: Doubling of direct bilirubin
	None	
	
If normal at baseline: ALT > 3 x ULN
 
If elevated at baseline: ALT > 2 x baseline or > 300 U/L (whichever occurs first)
	Normal or elevated	Severe fatigue, nausea, vomiting, right upper quadrant pain	

Table 16-3 Follow up requirements for liver laboratory triggers

Criteria	Actions required	Follow-up monitoring
Total Bilirubin (isolated)		
>1.5 – 3.0 ULN	
 • Maintain treatment • Repeat LFTs within 48-72 hours 	Monitor LFTs weekly until resolution ^c to ≤ Grade 1 or to baseline
> 3 - 10 × ULN (in the absence of known Gilbert syndrome)	
 • Interrupt treatment • Repeat LFT within 48-72 hours • Hospitalize if clinically appropriate • Establish causality • Record the AE and contributing factors (e.g. conmeds, med hx, lab) in the appropriate CRF 	Monitor LFTs weekly until resolution ^c to ≤ Grade 1 or to baseline (ALT, AST, total bilirubin, Alb, PT/INR, ALP and GGT) Test for hemolysis (e.g. reticulocytes, haptoglobin, unconjugated [indirect] bilirubin)
> 10 x ULN	
 • Discontinue the study treatment immediately • Hospitalize the participant • Establish causality • Record the AE and contributing factors(e.g. conmeds, med hx, lab)in the appropriate CRF 	ALT, AST, total bilirubin, Alb, PT/INR, ALP and GGT until resolution ^c (frequency at investigator discretion)
Any AE potentially indicative of a liver toxicity*	
 • Consider study treatment interruption or discontinuation • Hospitalization if clinically appropriate • Establish causality • Record the AE and contributing factors(e.g., conmeds, med hx, lab)in the appropriate CRF 	Investigator discretion
^a Elevated ALT/AST > 3 × ULN and TBL > 2 × ULN but without notable increase in ALP to > 2 × ULN ^b (General) malaise, fatigue, abdominal pain, nausea, or vomiting, or rash with eosinophilia ^c Resolution is defined as an outcome of one of the following: (1) return to baseline values, (2) stable values at three subsequent monitoring visits at least 2 weeks apart, (3) remain at elevated level after a maximum of 6 months, (4) liver transplantation, and (5) death.		

Based on investigator’s discretion investigation(s) for contributing factors for the liver event can include: Serology tests, imaging and pathology assessments, hepatologist’s consultancy; obtaining more detailed history of symptoms and prior or concurrent diseases, history of concomitant drug use, exclusion of underlying liver disease.

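### Potential Hy's Law and INR liver triggers are defined on ALT or AST, but the visible row that requires interruption is entered on ALT alone

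*Protocol*

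**What the plan says.** Protocol Section 9.1.1 refers the site to Section 16 for stopping treatment when a liver event occurs. In Section 16.2:

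- **Table 16-1 (triggers)** has nine entries, five of them on either transaminase. Two matter here: potential Hy's Law, "defined as ALT or AST > 3 × ULN and Total bilirubin > 2 × ULN" (with conditions on conjugated bilirubin and ALP), and "ALT or AST > 3 × ULN and INR > 1.5". For an abnormal baseline the trigger is "ALT or AST > 2x baseline or > 300 U/L (whichever occurs first").
- **Table 16-2 (actions)** has five rows under two block headings, "ALT increase without bilirubin increase" and "ALT increase with bilirubin increase". The enzyme column is headed ALT and every threshold in it is on ALT. The fourth row pairs the ALT threshold with "TBL > 2 x ULN (or INR > 1.5"). AST appears only as a follow-up measurement.
- **Table 16-3 (actions)** shows three rows for isolated total bilirubin and one for adverse events suggesting liver toxicity. The last asks the investigator to consider interrupting or stopping. Footnotes a (ALT/AST with raised bilirubin) and b (a symptom list) are printed below the table, but no visible row carries either marker.

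**The concern.** The trigger table treats the two enzymes as equal; the action table does not. For an ALT-driven case with raised bilirubin or INR, the site reads a definite rule: interrupt, retest within 48-72 hours, look for other causes, and resume only under stated conditions. For the AST-driven equivalent, the visible appendix recognises the trigger but prescribes no interruption. Two sites could therefore decide differently about the next biweekly dose for the same trigger. Section 6.6.2 describes this as the first repeat-dose study of the drug in this population, so the dosing rule for its most serious laboratory liver signals should not depend on which transaminase is the higher.

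**Working it through.** No sample size or error rate is involved. The check takes each trigger and asks which action row it opens.

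**Row count.** Table 16-2: 5 of 5 rows open on ALT, 0 of 5 on AST. Table 16-3: 0 of 4 visible rows open on AST.

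**Mirrored cases.** The values are illustrative. Only the enzymes are swapped between columns.

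| Case | ALT is the high enzyme | AST is the high enzyme |
|---|---|---|
| 1. Normal baseline; enzymes 4 and 2.5 × ULN; bilirubin 2.5 × ULN, mainly conjugated; ALP normal; no symptoms | Bilirubin/INR row: interrupt | No Table 16-2 row |
| 2. Normal baseline; enzymes 4 and 2.5 × ULN; bilirubin normal; INR 1.6; no symptoms | Bilirubin/INR row: interrupt | No Table 16-2 row |
| 3. Abnormal baseline; enzymes 2.5 and 1.5 × baseline, the lower one not above 300 U/L; bilirubin 2.5 × ULN | Bilirubin/INR row: interrupt | No Table 16-2 row |

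All six cells meet a Table 16-1 trigger. Two readings lie behind the ALT column. The blank action cells in rows 3 to 5 are taken as merged with the interruption instruction above them. In case 2, which also fits the first row (ALT > 3 × ULN, bilirubin normal, no symptoms), the more specific bilirubin/INR row is taken to govern.

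**Could Table 16-3 catch the AST cases?** Its bilirubin rows are for isolated elevation, so strictly they do not. If a site used them for want of anything closer, case 1 would fall in the band from 1.5 to 3.0 × ULN, where treatment is maintained. Above 3 × ULN the next band does call for interruption. The gap therefore matters most for bilirubin between 2 and 3 × ULN, and for INR cases with normal bilirubin. The liver adverse-event row can apply to an AST case, but it leaves interruption to judgement and needs the case to be classed as such an event.

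**After the fix.** With entry on ALT or AST, cases 1 to 3 fall in the same row whichever enzyme is high. This follows directly from the wording change.

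**The case against.** **Text may be missing.** Footnotes a and b suggest that Table 16-3 once had, or still has, rows for ALT/AST with raised bilirubin and for symptoms. It would be uneven to repair the blank cells of Table 16-2 and ignore this. It stands as a real limit: if a row carrying footnote a exists, the Hy's Law case may be covered. Neither footnote mentions INR, so on that assumption the INR case stays open.

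**Rules may sit in redacted text.** Section 4.5 says the protocol contains dose-limiting toxicity definitions and dosing-holiday guidance. Parts of 6.5 and 6.6.2 and the text after 10.2 are redacted. This also stands. The point concerns the visible appendix, to which 9.1.1 sends the site, and does not show that the full plan lacks a rule.

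**Safeguards exist.** A reader might infer that AST-driven cases have no prescribed action at all. The documents do not support that. The liver adverse-event row requires causality to be established and the event recorded. Section 9.1.1 requires treatment to stop for a safety risk or for a laboratory abnormality that the investigator judges disqualifying. Section 8.4.1 makes repeat testing mandatory for laboratory adverse events, and 9.3 lets the sponsor place enrollment on hold. What is missing is a visible AST threshold that requires interruption.

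**ALT-only entry may be intended.** Table 16-2 does not map one-to-one onto Table 16-1 even for ALT. Its symptom row ("Severe fatigue, nausea, vomiting, right upper quadrant pain") is narrower than the trigger ("ALT or AST > 3 × ULN accompanied by (general) malaise, fatigue, abdominal pain, nausea, or vomiting, or rash with eosinophilia"), and its first row opens at a level that is not by itself a normal-baseline trigger. That weakens any demand for full symmetry. It does not explain why a potential Hy's Law or INR case should be handled differently by enzyme, and no visible text says so.

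**The mirrored cases only restate the wording.** True. They locate the gap and say nothing about how often it would occur.

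**Conclusion.** The mismatch holds for two of the five ALT-or-AST triggers, potential Hy's Law and INR, and for an abnormal-baseline AST rise combined with bilirubin > 2 × ULN or INR > 1.5. In these cases the ALT-driven participant has a prescribed interruption and the AST-driven one has only discretionary cover.

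A reader might infer that all five triggers lose an interruption. They do not. A newly found isolated rise, or an abnormal-baseline rise alone, starts on the ALT side with treatment unchanged and a retest, so the AST case at first lacks only that specified retest. The symptom trigger does show the same ALT-only entry, but extending interruption there is more debatable: nausea and vomiting can have other causes (Section 8.1.1.3 notes this for vaccination), and an AST rise need not be hepatic.

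The conclusion rests on the visible text and on the merged-cell reading of Table 16-2. Confidence is medium because lost or redacted text could cover part of the gap. The documents give no expected number of AST-driven cases. It is a specific and inexpensive safety correction worth making, and it does not show that such participants would go unmanaged.

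**What to change.** First check the original of Table 16-3 for rows carrying footnotes a and b. If there are none, delete or reattach the footnotes.

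Then change the entry of the Table 16-2 bilirubin/INR row from ALT to ALT or AST, for both normal and elevated baseline, with the same interruption, work-up and restart rule. Amend the block heading to match.

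Optional: extend the change to the symptom row and the isolated-rise rows, with CK used to exclude AST of muscle origin. Extending the first row would also give AST-only rises the 48-72 hour retest, which includes INR.

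**Cost.** Appendix wording in the next amendment. AST, bilirubin, CK and INR are all listed in Table 8-3. There may be a few more interruptions; how many cannot be derived from the documents. Restart requires both another cause and a return of enzymes to baseline, so an interruption could end treatment. One participant is 1/12 = 8.3% of an arm's planned completers. The week 16 weight need not be lost, because Section 9.1.1 asks participants who stop treatment to keep attending assessments where possible.

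### Table 16-2's immediate interruption limit for an isolated ALT rise covers normal baseline ALT only; with raised baseline ALT the table allows about one further dose before it requires a stop

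*Protocol*

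**What the plan says.** Table 16-2 has five ALT rows. Three deal with an ALT rise without a bilirubin rise and without symptoms.

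- The first covers raised baseline as "If elevated at baseline: ALT > 2 x baseline or > 300 U/L (whichever occurs first", and its action begins "No change to study treatment". A liver panel follows in 48–72 hours, with follow-up for symptoms.
- The second covers raised baseline as "If elevated at baseline: ALT > 3 x baseline or > 300 U/L (whichever occurs first) for more than two weeks". Its action is to interrupt, with close monitoring and a work-up. It also sets the restart rule: "Study drug can be restarted only if another etiology is identified and liver enzymes return to baseline".
- The third reads "If normal at baseline: ALT > 8 x ULN". It has no duration condition and no line for raised baseline.

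The last two rows cover both kinds of baseline and have no duration condition, but each needs something more than ALT: "TBL > 2 x ULN (or INR > 1.5" (or a doubling of direct bilirubin in Gilbert's syndrome) in one, and "Severe fatigue, nausea, vomiting, right upper quadrant pain" in the other.

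Table 16-1 defines a separate trigger for abnormal baseline, "ALT or AST > 2x baseline or > 300 U/L (whichever occurs first", but attaches no treatment action to it. Section 9.1.1 requires study treatment to stop when the investigator judges that continuing would harm the participant's well-being, that there is a safety risk, or that a laboratory abnormality rules out continuing. For liver events it refers to Section 16.

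**The concern.** Four of the five ALT rows give a limit for raised baseline; only the > 8 × ULN row does not. That row treats an isolated, asymptomatic ALT as high enough, on level alone, to stop dosing without waiting to see whether it persists. At the same ALT, a participant with raised baseline meets no level in the table that has this effect. The 300 U/L alternative does not help, because it appears both in the row that continues treatment and in the row that interrupts it. Above 300 U/L, only elapsed time separates the two.

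At stake is continued dosing during a marked transaminase rise, in what Section 6.6.2 describes as the first repeat-dose study of MBL949 in this population. Participants with raised baseline ALT are plausible: Tables 16-1 and 16-2 both provide for them, and Section 1.1 links obesity with liver disease, including non-alcoholic fatty liver disease.

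**Working it through.** **1. The ALT rows of Table 16-2 side by side** (limits in U/L where no multiple is given).

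| Row | Normal baseline | Raised baseline | Also required | Action |
|---|---|---|---|---|
| 1 | > 3 × ULN | > 2 × baseline or > 300 | – | continue, recheck |
| 2 | > 5 × ULN, over two weeks | > 3 × baseline or > 300, over two weeks | – | interrupt |
| 3 | > 8 × ULN | no entry | – | interrupt* |
| 4 | > 3 × ULN | > 2 × baseline or > 300 | bilirubin or INR | interrupt* |
| 5 | > 3 × ULN | > 2 × baseline or > 300 | symptoms | interrupt* |

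*Action cell empty in the text as read; taken as merged with row 2. In the raised-baseline column, no ALT level on its own leads to interruption until two weeks have passed.

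**2. Example.** ULN is not in the documents. Assume 40 U/L, so 8 × ULN = 320 U/L (range 8 × 35 = 280 to 8 × 55 = 440). Take an isolated ALT of 400 U/L.

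- Baseline 38 (normal): 400 > 320, so row 3 applies and dosing is interrupted at once.
- Baseline 50 (raised): 400 > 2 × 50 = 100, so row 1 applies and treatment continues. Also 400 > 3 × 50 = 150, but row 2 requires interruption only after more than 14 days.

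This pair of baselines illustrates the point for any ULN from 38 to just under 50. Other ULNs move the numbers but not the structure.

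**3. Doses given while waiting.** The plan's schedule reproduces: Day 1 + 14k for k = 0 to 7 gives Days 1, 15, 29, 43, 57, 71, 85 and 99, which is eight doses over (99 − 1)/7 = 14 weeks. Table 8-1 schedules post-dose chemistry on Days 10, 15, 29, 43, 57, 71, 85 and 99 within the treatment period. Section 8.4.1 sends samples to a central laboratory, so a dose on the day of sampling is taken as already given. Count the doses after finding day t and no later than t + 14:

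- t = 10: Day 15 only (Day 29 is 19 days on).
- t = 15, 29, 43, 57, 71 or 85: the next dose, exactly 14 days on, which is not yet more than two weeks. Found on Day 29, Day 43 is given and Day 57 withheld.
- t = 99: none.

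That is one further dose for seven of the eight finding days, or 1/8 = 12.5% of the course. Starting the two weeks at the recheck (t + 2 or t + 3) gives the same counts. A visit window can remove the dose if the clock starts on the day the rise is detected: with the ±1 day printed for Day 57, 58 − 43 = 15 > 14.

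**4. Choosing the missing limit.** Copying > 8 × ULN across unchanged can stop dosing on a trivial rise. At ULN 40 and baseline 250, an ALT of 321 exceeds 320 but is only 321/250 = 1.28 × baseline. Adding > 300 U/L does not help, since 321 exceeds that too. Adding > 3 × baseline does:

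- The limit becomes max(8 × ULN, 3 × baseline). At baseline 250 this is max(320, 750) = 750.
- At baseline 50 it is max(320, 150) = 320, so the 400 U/L example is caught.
- max(8 × ULN, 3 × baseline) ≥ 3 × baseline ≥ min(3 × baseline, 300) ≥ min(2 × baseline, 300). It is therefore never below any other raised-baseline limit in the table.

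**The case against.** The strongest reply is that the gap may be closed in text that cannot be seen. Section 4.5 says the protocol contains dose-limiting-toxicity definitions and guidelines for dosing holidays. Section 6.5 on dose modification is largely redacted, as are most exclusion criteria, and a cap on baseline ALT could leave nobody affected. This stands. A reader might infer that the protocol has no immediate stop for these participants; the documents do not support that, and the point is limited to what Table 16-2 requires.

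Second, the reading of row 3 rests on an empty cell in a table that may be broken. A merged interruption cell is the natural reading, but it is a reading. The row also lacks the Gilbert's line, so it may be short on purpose.

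Third, the uncovered case is narrow. Any bilirubin, INR or listed symptom change brings in rows 4 and 5 at once, at lower ALT limits. The 48–72 hour recheck normally falls before the next biweekly dose. An investigator seeing 400 U/L may well stop under Section 9.1.1, or treat it as a liver-toxicity event, for which Table 16-3 advises considering interruption. All true, but none of these supplies an ALT number, and Section 9.1.1 sends liver events back to the section whose immediate instruction is to continue.

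Fourth, judging raised-baseline participants by change from baseline, with a check on persistence, is clinically reasonable: at ULN 40 and baseline 160, 8 × ULN is only 2 × baseline. This is a sound argument against copying 8 × ULN across unchanged. It does not explain why there should be no upper level at all.

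Nor does the table favor normal-baseline participants throughout. At ULN 40 and baseline 50, the raised-baseline limits in rows 1 and 2 (100 and 150) are below the normal-baseline ones (120 and 200). The asymmetry lies in row 3 alone.

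**Conclusion.** The point holds for Table 16-2. With raised baseline ALT, normal bilirubin, INR not above 1.5 and no listed symptoms, no ALT level triggers interruption under the table until more than two weeks have passed. On nominal days that is about one further dose of eight, or none if the rise is first found on Day 99.

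This assumes the merged-cell reading of the action column, an ALT that stays raised, no change in bilirubin, INR or symptoms, and no hold by the investigator. The ULN values are assumed and affect only the illustration. How many participants would be affected cannot be derived.

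A reader might go further and conclude that dosing must continue at a dangerous ALT. The documents do not say so: Section 9.1.1 obliges the investigator to stop on a judged risk, and redacted text may add a hold. What is missing from the table is a number. This is a worthwhile and inexpensive improvement to a safety rule, held with medium confidence.

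**What to change.** Add to the > 8 × ULN row of Table 16-2 the line *If elevated at baseline: ALT > 8 × ULN and > 3 × baseline*, with no duration condition and the same action as for normal baseline. If redacted text already provides an immediate hold for these participants, a cross-reference in the row is enough.

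The cost is one table entry at the next amendment, with no new tests or visits. The downside is a few extra interruptions in participants with raised baseline ALT. The existing restart rule would apply to them and is strict, so some may not resume treatment.
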